9.4.3 ANALYSIS OF THE SECONDARY OUTCOME VARIABLE(S)

- Resolution of EPL
 - Binomial outcome: Absence of gestational sac on transvaginal ultrasound examination on Day 3 follow up
 - o Binomial outcome: Need for additional dose of misoprostol within 30 days of treatment
 - Binomial outcome: Need for uterine aspiration within 30 days of treatment
- Side Effects/Adverse Events
 - Side Effects Binomial Outcomes (N, %)
 - Fatigue
 - Headache
 - Dizziness or lightheadedness
 - Chills
 - Nausea
 - Diarrhea
 - Vomiting
 - Severe cramping
 - Fever
 - Other
 - Adverse Events Binomial Outcomes (N, %)
 - Excess bleeding requiring blood transfusion
 - Pelvic infection requiring antibiotics
- Patient Acceptability
 - Likert Scale Ordinal Outcomes (Median, Counts)

- Would you use this combination of medications again if you had another early pregnancy loss?
- Would you recommend this combination of medications to a friend with early pregnancy loss?
- If it was possible to take the first medication at home (versus in clinic), would you be more or less likely to use this combination of medications again?
- If it were possible to take the first medication at a different time (versus during your appointment), would you be more or less likely to use this combination of medications again?

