1.3 SCHEDULE OF ACTIVITIES (SOA)

Procedures	Screening Visit 1, Day 0	Enrollment/Baseline Visit 1, Day 0	At Home Day 0	Study Visit 2 Day 3 +/- 1day	Study Visit 3 Day 8 +/- 1 day	Lab Testing Day 14 +/- 1 day	Study Visit 4 Day 30 +/- 7 days
Eligibility criteria	Х						
Informed consent	Х						
Demographics questionnaire	Х						
Administer UPA		Х					
Patient self-administers			Х				
misoprostol							
Physical exam	Х						
Vital signs	Х			Х	Х		
Hemoglobin and ABO/Rh testing	Х						
Liver function testing	Х					Х	
Adverse event review and evaluation	Х			х	Х		Х
Radiologic/Imaging assessment	Х			Х	Х		
Treatment success questionnaire completed by MD				Х	Х		
Offer additional intervention if needed if gestational sac still present				Х	Х		
Additional treatment questionnaire							Х
Side effects and adverse events questionnaire				х	х		Х
Patient acceptability questionnaire							Х

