3 OBJECTIVES AND OUTCOMES

OBJECTIVES	OUTCOMES	JUSTIFICATION FOR
		OUTCOMES
Primary		
To assess whether it is feasible to study UPA plus misoprostol as an intervention for medical management of EPL for larger future studies.	Recruitment: number of participants in study/number of patients screened for participation Adherence: number of participants adhering to study intervention (UPA + misoprostol vaginally after 6-18 hours)/number of participants in study Retention: number of participants	Study outcomes of interest for feasibility based on outcomes of interest appropriate for pilot studies [24-26].
	attending all study visits (day 0, 3/8, 30)/number of participants in study	
Secondary	30)/ Humber of participants in study	
Secondary		

OD LECTIVIES	OUTCON AEC	U (CT) 5 (CA T) CA L 5 C C
OBJECTIVES	OUTCOMES	JUSTIFICATION FOR
		OUTCOMES
To evaluate if participants taking UPA plus misoprostol achieve complete resolution of EPL.	Absence of gestational sac on transvaginal ultrasound examination on Day 3 follow up	Same outcome was used in randomized controlled trial of mifepristone plus misoprostol for early pregnancy loss to calculate effective intervention [2].
To investigate if UPA plus misoprostol is associated with side effects or adverse events when used for EPL.	Participants self-report of side effects or adverse events following UPA and misoprostol.	Study outcomes of interest for feasibility based on outcomes of interest appropriate for pilot studies [24-26].
To identify if UPA plus misoprostol is acceptable to patients for treatment for EPL.	Participants willing to use this combination of medication again for another early pregnancy loss or recommend this combination of medications to a friend.	

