Follow up of medical management of EPL generally consists of confirmation of pregnancy expulsion by ultrasound examination or serial beta-hCG measurements in settings where ultrasound is not available [1]. There is no standard of care regarding specific intervals when ultrasonography or laboratory follow up assessment should take place. Study follow up schema for our study is based on participant follow up design from a similar study of mifepristone and misoprostol for EPL [2].

Participants will follow up with the UNC Family Planning Division for a transvaginal ultrasound on study day 3 to ensure expulsion of the gestational sac. Women generally experience cramping and vaginal bleeding 1 to 4 hours following misoprostol administration and pass their pregnancy within 24 hours of starting to bleed. Thus, follow up on day 3 will assess participants who are able to pass their pregnancy with a single dose of UPA and misoprostol.

For those who still have a pregnancy in the uterus, they will be offered an additional dose of 800mcg misoprostol, expectant management, or surgical management. Those who did not have expulsion of the pregnancy on day 3 and elect for an additional dose of misoprostol or expectant management will follow up with the UNC Family Planning Division for another transvaginal ultrasound on study day 8 to ensure expulsion of the gestational sac. As some studies of EPL assess for response 7 days after medication administration, we will be able to compare our data to similar studies through our day 8 follow up results [3]. Further, twenty-five to thirty percent of EPL will pass with expectant management alone one week after diagnosis [27].

Participants will be assessed for possible liver toxicity on study day 14 through a laboratory test of ALT, AST and total bilirubin.

All study participants will receive a phone call on study day 30 to what additional treatment patients needed for their early pregnancy loss, investigate any side effects or adverse events, and identify acceptability of the treatment. Most symptoms of bleeding and abdominal cramping following medical management of EPL occur in the first two to four weeks following medication administration; thus, 30 days is an adequate time to assess for side effects and acceptability of treatment while not being too remote from the time of the pregnancy passing.

A detailed description of all study visits is provided below:

Visit 1 (Day 0):

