- Participant is screened for eligibility by the study coordinator and offered admission to study if eligible
 - Review of radiologic imaging to confirm early pregnancy loss based on eligibility criteria
 - Review of physical exam findings and vital signs (heart rate, blood pressure, temperature) to ensure that patient is hemodynamically stable and not having an inevitable or incomplete abortion based on eligibility criteria
- Participant reviews and signs informed consent and HIPAA authorization form
- Participant completes paper baseline demographic questionnaire
- Participant will have hemoglobin, ABO/Rh status and liver function testing (ALT, AST, total bilirubin) if not already performed by primary OBGYN

 Participant takes 90mg ulipristal acetate with study team; given prescription for 800mcg misoprostol to take at home

Visit 2 (Day 3 ± 1 day):

- Participant returns to UNC Family Planning Clinic
- Participant has vital signs checked by RN at clinic
- Participant fills out questionnaire regarding bleeding symptoms and any side effects or adverse
 events after taking the ulipristal acetate and misoprostol, including reporting time and route of
 administration of misoprostol at home
- Participant has a transvaginal ultrasound completed by the principal investigator to ensure that the pregnancy has passed (no gestational sac visualized on ultrasound)
- If pregnancy is still in the uterus, patient will be offered surgical management, medical management (an additional dose of misoprostol 800mcg), or expectant management

Visit 3 (Day $8 \pm 1 \text{ day}$):

- Participant will only attend this visit if a gestational sac was still present on ultrasound on Visit
 2 and patient opted for medical management or expectant management. If gestational sac is absent at Visit 2, participant will not need Visit 3. All participants will complete Visit 4.
- Participant returns to UNC Family Planning Clinic
- Participant has vital signs checked by RN at clinic
- Participant fills out questionnaire regarding bleeding symptoms and any side effects or adverse events after taking the ulipristal acetate and misoprostol
- Participant has transvaginal ultrasound completed by the principal investigator to ensure that the pregnancy has passed (no gestational sac visualized on ultrasound)
- If pregnancy is still in the uterus, patient will be offered surgical management, medical management (if patient did not receive additional misoprostol at Visit 2), or expectant management

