6.1.2 DOSING AND ADMINISTRATION

Participants will be given 90mg UPA (three 30mg oral tablets) in the presence of research staff on baseline/enrollment visit 1 (day 0) after determining eligibility and giving informed consent. Patients will be prescribed 800mcg misoprostol (four 200mcg tablets) and instructed to self-administer misoprostol vaginally 6 to 18 hours after administration of UPA. Participants will be given oral medications to manage pain and symptoms during their EPL from their OBGYN provider prior to discharge home.

Medication timing of misoprostol administration will be based on post-hoc analysis of misoprostol administration following mifepristone for early pregnancy loss. These data suggest that patients have the highest likelihood of success when misoprostol is administered 7 to 20 hours after mifepristone [32]. Pharmacokinetic data suggest that peak concentrations of ulipristal acetate and its active metabolite are 0.9 hours and 1 hour respectively, compared to mifepristone that reaches peak concentrations after 90 minutes; thus we propose earlier times when compared with those recommended with mifepristone [16,17]. Further, extensive data has studied vaginal misoprostol 6 hours after mifepristone for medication abortion with good success [33].

If a gestational sac is still present on transvaginal ultrasound on visit 2 (day 3), expectant management, medical management or surgical management will be offered to patients. Patients desiring additional medical management will be instructed to administer 800mcg misoprostol vaginally or buccally within 24 hours of their appointment. Patients may not be eligible for additional dosage of misoprostol if they are hemodynamically unstable and necessitate urgent or emergent surgical intervention.

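### Day 3 resolution is scored on sac absence alone: a woman aspirated before the scan is not counted as a failure, and no outcome measures resolution without intervention

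*Combined protocol and SAP*

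**What the plan says.** Section 3 of the combined protocol and SAP gives the objective as "To evaluate if participants taking UPA plus misoprostol achieve complete resolution of EPL". The one outcome set against it is absence of a sac on the Day 3 scan, justified as the outcome used in the cited randomized trial of mifepristone plus misoprostol. Section 9.4.3 repeats it: "Binomial outcome: Absence of gestational sac on transvaginal ultrasound examination on Day 3 follow up". Under the same heading it lists two further items, "Binomial outcome: Need for additional dose of misoprostol within 30 days of treatment" and "Binomial outcome: Need for uterine aspiration within 30 days of treatment". No rule connects the three.

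Section 4.1 gives the purpose of the visit: "follow up on day 3 will assess participants who are able to pass their pregnancy with a single dose of UPA and misoprostol".

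Section 9.3 limits the main analysis of secondary endpoints to participants who adhered to study medication and completed all visits. A sensitivity analysis takes all enrolled participants with available data. Section 9.4.8 rules out individual listings, and Section 9.4.9 rules out additional exploratory analyses.

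The Schedule of Activities (Section 1.3) places a physician-completed treatment success form, an adverse event review and a side effects questionnaire at Visit 2. The "Additional treatment questionnaire" appears only at Visit 4, the Day 30 call.

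**The concern.** The stated purpose of the Day 3 visit and the scoring rule differ. The purpose is about how the pregnancy passed. The rule asks only what the scan shows. They agree for most women and part company for a woman whose uterus was emptied by aspiration before the scan. She is a clear failure of the regimen, yet the rule either credits her to it or loses her.

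The second gap concerns the words complete resolution in the objective. A reader planning the larger trial will want the number of women who needed nothing beyond UPA and one dose of misoprostol. The plan reports three separate proportions and no combination of them.

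**Working it through.** **1. The plan's own figure.** The only design number is the enrolment of 40 (Section 9.2). Applying 300/800 = 37.5% to about 100 diagnoses gives 37.5, or 38. Applying it to two per week for 52 weeks gives 104 × 0.375 = 39. Both are close to 40. The point does not depend on this figure.

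**2. How the written rules score each woman.** This assumes that an aspiration empties the uterus and that she is otherwise adherent and completes follow-up.

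| Woman | Main analysis | Sensitivity analysis |
|---|---|---|
| Aspirated before the scan, attends Visit 2 | Success | Success |
| Aspirated before the scan, misses Visit 2 | Excluded (visits incomplete) | No Day 3 result |
| No sac on Day 3, aspirated later | Success at Day 3; counted separately under aspiration | Same |
| Sac on Day 3, then aspirated | Failure | Failure |

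The last row is right. The third is right as a Day 3 statement. The first two never yield a failure.

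**3. Effect per woman.** The documents give no rate of aspiration before the scan, so only the effect of one woman can be stated.
- She attends and is reclassified: 1/40 = 2.5 points. If adherence is at the 50% threshold of Section 9.1, the main set is about 40 × 0.5 = 20, and 1/20 = 5 points.
- She misses the scan and is restored as a failure: with an assumed 32 sac-free among 39 scanned, 32/39 = 82.1% becomes 32/40 = 80.0%, a change of 2.1 points. With 16 among 19, 84.2% becomes 16/20 = 80.0%, a change of 4.2 points.

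Illustration with exact (Clopper-Pearson) 95% intervals, assuming 80% are sac-free and k of them were aspirated before the scan:

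| k | n = 40 | n = 20 |
|---|---|---|
| 0 | 32/40 = 80.0% (64.4–90.9) | 16/20 = 80.0% (56.3–94.3) |
| 1 | 31/40 = 77.5% (61.5–89.2) | 15/20 = 75.0% (50.9–91.3) |
| 2 | 30/40 = 75.0% (58.8–87.3) | 14/20 = 70.0% (45.7–88.1) |

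The shifts are small beside the width of the intervals, but they all run in one direction.

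**4. What the separate counts can show.** Let S be the number sac-free on Day 3, A the number aspirated by Day 30, and n the number analysed. The overlap lies between max(0, S + A − n) and min(S, A). With assumed S = 32, A = 4 and n = 40, that is 0 to 4. Resolution without aspiration is then S minus the overlap, anywhere from 28/40 = 70.0% to 32/40 = 80.0%. The published counts cannot narrow this range. The additional-misoprostol count brings a second unknown overlap, though the plan offers that dose only after a sac has been seen, so it should be small. The investigator will hold the data to resolve this, but the plan does not provide for the analysis.

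**The case against.** Several arguments against the point have force.

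- **The later aspiration.** A reader might infer that a woman with an empty Day 3 scan and a later aspiration is misclassified. She is not. The outcome is a time-point measure, she had no sac at that time, and her aspiration is reported under the same Resolution of EPL heading. What stands is only that no composite is defined.
- **A definite inflation.** A reader might infer that the reported rate will be several points too high. The documents do not support any such figure. It would need an assumed number of women, would pool early and late aspirations although only the early ones affect Day 3, and would use 40 as the denominator when the main set is smaller. Section 8.3.6 gives about 1% for severe adverse events, or 0.4 women in 40. That is not an aspiration rate, but it does not suggest many urgent cases.
- **Section 6.1.2.** Its reference to women who may not receive a second misoprostol dose "if they are hemodynamically unstable and necessitate urgent or emergent surgical intervention" could be read as showing that the plan expects evacuation before the scan. In context it concerns women who still have a sac at Visit 2, and they are already failures.
- **Data capture.** A reader might infer that Visit 2 has no means of recording an earlier intervention. The forms are not shown, so this cannot be said. Adverse event review, chart alerts and chart abstraction (Sections 8.1, 8.3.4 and 8.3.5) would probably reveal an aspiration done at the site. Knowing of it would not change her score, however, because no rule uses the information.
- **Extra misoprostol before the scan.** Section 9.3 classes any other timing of study medication as non-adherent, so the main analysis largely deals with this already. The sensitivity analysis does not.
- **Comparability.** Sac absence was chosen to match a cited trial. Whether that trial also required no intervention cannot be checked here. In either case the mismatch with Section 4.1 remains.

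**Conclusion.** The point holds in a limited form. As written, the Day 3 outcome does not carry the single-dose condition that Section 4.1 states, and a woman aspirated before the scan counts either as a success or not at all. Separately, the plan cannot report how many women achieved complete resolution without intervention.

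The size is 2.5 points per woman who attends the scan at n = 40, or 5 points in a main set of about 20. It is slightly less for a woman who misses the scan and is restored as a failure. These figures assume that the aspiration left no visible sac. The number of such women is unknown and may be zero. No test or error rate is affected, because the outcome is secondary, hypothesis-generating and descriptive. The change is still worth making. The rule mis-scores the clearest regimen failures, always in the favourable direction, and the result is meant to inform a larger trial.

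**What to change.** 1. In Sections 3 and 9.4.3, define Day 3 success as no gestational sac at Visit 2 and no uterine aspiration or additional misoprostol before that scan. Score an earlier intervention as failure whether or not the scan is attended.
2. In Section 9.3, state that missing Visit 2 does not remove a woman with such an intervention from the analysis of this outcome.
3. Confirm that the Visit 2 physician form records any intervention since UPA, with type and date, or add that item. Confirm that the Day 30 questionnaire also captures dates, so that a woman who missed Visit 2 can be scored.
4. Add to Section 9.4.3 a Day 30 composite: Day 3 success with no later aspiration or additional misoprostol, using the Day 30 questionnaire already scheduled.
5. Keep sac absence alone as a descriptive line for comparison with the cited trial.

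The cost is a few sentences and at most one or two items on existing forms. No visit, procedure or aspect of care changes. The downside is that the reported success rate may be slightly lower.

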2.3 RISK/BENEFIT ASSESSMENT

2.3.1 KNOWN POTENTIAL RISKS

Ulipristal acetate is a 30mg tablet progesterone receptor agonist/antagonist that was FDA approved for emergency contraception in 2010. Adverse events noted from an open-label multicenter trial and a randomized, single-blind multicenter trial include headache (18%), nausea (12%), and abdominal pain (12%). Other less common side effects include dysmenorrhea, fatigue and dizziness. Post marketing experience has also shown an increase in acne among users of the medication [16].

This study will be utilizing a dosage of UPA 90mg to most closely match the effects of mifepristone 200mg, which is the dosage studied for EPL based on a study of endometrial histology showing similar effects of UPA 100mg to mifepristone 200mg [2,19]. FDA approval indicated that experience with single dose equivalent of up to four times the standard UPA dose were administered to a limited number of subjects without any adverse reactions, suggesting that UPA 90mg may be used safely in this patient population [16]. In a pilot study of ulipristal acetate 90mg at the dose that would be used for this study, no significant adverse events were noted [23].

Additionally, there will be two blood draws required for the study to monitor liver function testing. Possible risks of these blood draws include mild risks of pain, bruising and fainting. These risks are infrequent, and all lab draws will be completed by clinic nurses or the study coordinator, who have been trained in phlebotomy.

Possible psychologic risks of the study include consequences of breach of confidentiality. All study materials will be kept solely with research staff. All medical care will be documented in the UNC EPIC system, which has safeguards to reduce the risk of confidentiality breaches.

Possible social risk includes the risk of stigmatization of UPA if used in the context of EPL. Just as mifepristone is known as the "abortion pill", making it less likely to be used in other settings, UPA may undergo similar stigmatization, which may change prescribing patterns of UPA.

Possible economic risks include loss of income and time for follow up appointments, as patients undergoing medication management of EPL generally are followed up with a phone call as opposed to an in-person appointment. Patients will be compensated for their travel time and will not have to pay for their follow up visits.

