8.3.4 TIME PERIOD AND FREQUENCY FOR EVENT ASSESSMENT AND FOLLOW-UP

The occurrence of an adverse event (AE) or serious adverse event (SAE) may come to the attention of study personnel during study visits and interviews of a study participant presenting for medical care, or upon review by a study monitor.

All AEs including local and systemic reactions not meeting the criteria for SAEs will be captured on the appropriate case report form (CRF). Information to be collected includes event description, time of onset, clinician's assessment of severity, relationship to study product (assessed only by those with the training and authority to make a diagnosis), and time of resolution/stabilization of the event. All AEs occurring while on study must be documented appropriately regardless of relationship. All AEs will be followed to adequate resolution.

Any medical condition that is present at the time that the participant is screened will be considered as baseline and not reported as an AE. However, if the study participant's condition deteriorates at any time during the study, it will be recorded as an AE.

Changes in the severity of an AE will be documented to allow an assessment of the duration of the event at each level of severity to be performed. AEs characterized as intermittent require documentation of onset and duration of each episode.

The study sponsor will record all reportable events with start dates occurring any time after informed consent is obtained until 7 (for non-serious AEs) or 30 days (for SAEs) after the last day of study participation. At each study visit, the investigator will inquire about the occurrence of AE/SAEs since the last visit. Events will be followed for outcome information until resolution or stabilization.

All participants in the study will have notation on their UNC EPIC chart to alert the research staff if the patient is seen for any possible adverse event. Patients will be assessed for adverse events at their telephone follow up 30 days after study intervention. Solicited information on adverse events will include increased bleeding requiring hospital admission or blood transfusion and infection requiring hospital admission or IV antibiotics. All other adverse events will be identified based on unsolicited questioning during this telephone visit.

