8.3.6 SERIOUS ADVERSE EVENT REPORTING

Based on prior studies of mifepristone and misoprostol, the rate of severe adverse event in this population is extremely low (approximately 1%). The study clinician will immediately report to the sponsor any serious adverse event, whether the adverse event is considered study intervention related, including those listed in the protocol and must include an assessment of whether there is a reasonable possibility that the study intervention caused the event. Study outcomes that are serious adverse events (e.g., all-cause mortality) must be reported in accordance with the protocol unless there is evidence suggesting a causal relationship between the study intervention and the event (e.g., death from anaphylaxis). In that case, the investigator must immediately report the event to the sponsor.

All serious adverse events (SAEs) will be followed until satisfactory resolution or until the site investigator deems the event to be chronic or the participant is stable. Other supporting documentation of the event may be requested by the study sponsor and should be provided as soon as possible.

Upon the first severe adverse event that occurs among study participants, the study will be stopped temporarily until review of the event by the UNC IRB. Following review of the severe adverse event, a decision will be made if the entire study will need to be stopped prematurely or if it is safe to continue the study.

The study sponsor will be responsible for notifying the Food and Drug Administration (FDA) of any unexpected fatal or life-threatening suspected adverse reaction as soon as possible, but in no case later than 7 calendar days after the sponsor's initial receipt of the information. In addition, the sponsor must notify FDA and all participating investigators in an Investigational New Drug (IND) safety report of potential serious risks, from clinical trials or any other source, as soon as possible, but in no case later than 15 calendar days after the sponsor identifies that the information qualifies for reporting.

Any serious liver injury case consistent with Hy's law will be reported as an expedited report to the FDA.

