9.2 SAMPLE SIZE RATIONALE

As this is a feasibility pilot study, no formal power calculation is required. We anticipate recruiting a convenience sample of 40 participants over the course of 12 months recruitment based on prior information from UNC Chapel Hill where approximately two patients with EPL are diagnosed per week at our two study locations after accounting for eligibility criteria and desire participation in the study. We estimate that of the approximately 100 patients diagnosed with EPL over the year, 40 patients will enroll given prior recruitment rates from studying mifepristone and misoprostol for early pregnancy loss (800 EPL patients for a total of 300 participants) [2].

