9.4.9 EXPLORATORY ANALYSES

No additional exploratory analyses will be completed.

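### Bleeding-symptom answers collected at Visits 2 and 3 have no planned summary, and the one named bleeding outcome (transfusion) is rare and narrower than what is asked at day 30

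*Combined protocol and SAP*

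**What the plan says.** **Collection.** The visit descriptions in 4.1 state, for both Visit 2 and Visit 3: "Participant fills out questionnaire regarding bleeding symptoms and any side effects or adverse" events. Bleeding symptoms are thus named separately from side effects. Visit 3 is attended only by women whose sac was still present at Visit 2 and who chose medical or expectant management. At the day 30 call, 8.3.4 solicits "increased bleeding requiring hospital admission or blood transfusion".

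**Analysis.** Section 9.4.3 lists nine named side effects plus an Other category, none of them bleeding. It lists two adverse events, of which the bleeding one is "Excess bleeding requiring blood transfusion". Section 9.4.4 reports every side effect and adverse event not listed in 9.4.3 by frequency and percentage, and gives severity and relatedness for the other adverse events. Section 9.4.1 attaches 95% confidence intervals to all statistics. Section 9.4.9 adds: "No additional exploratory analyses will be completed".

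**Population.** Under 9.3, the secondary endpoints, including side effects and adverse events, are analysed in participants who adhered to study medication and completed all visits. A sensitivity analysis takes all enrolled participants with data.

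**The concern.** One secondary objective is to find out whether UPA plus misoprostol is associated with side effects or adverse events, measured by self-report (section 3). By 4.2 this is the first study of UPA for this indication. Women are asked about bleeding, yet no line of the plan commits to summarising the answers. The outcome that is named will probably be zero whatever the regimen does.

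Two further features weaken it. A woman admitted for bleeding but not transfused gives a positive answer to the 8.3.4 question and falls outside the 9.4.3 outcome. And the main analysis leaves out non-adherent women and those who missed a visit. A woman who bled after UPA and did not take misoprostol in the window, or who was lost after a bleed, would appear only in the sensitivity analysis, and only if her data were available.

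At stake is what the pilot can tell the planners of the larger trial about bleeding, and whether bleeding measures are chosen before or after the answers are seen.

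**Working it through.** **Inputs**
- Sample size, from 9.2: "We anticipate recruiting a convenience sample of 40 participants". There is no power calculation. The basis is the prior study's recruitment, "800 EPL patients for a total of 300 participants".
- Rate of any severe adverse event in prior mifepristone and misoprostol studies, from 8.3.6: about 1%.
- Transfusion rate: not given. Assumption: transfusion is one component of that 1%, so 1% is a ceiling. Range used: 0.25% to 1%.
- Size of the main analysis set: 9.1 sets adherence at more than 50%, so about 0.50 × 40 = 20 women at that threshold, before any loss for missed visits.

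**Step 1. The plan's own figure.** 300/800 = 37.5%. Applied to about 100 patients a year this gives 37.5; applied to 2 × 52 = 104 it gives 39. Both are close to the stated 40.

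**Step 2. Expected transfusions in 40 women.** Expected count = n × p; chance of none = (1 − p)^n.

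| Assumed rate | Expected count | Chance of none |
|---|---|---|
| 1% | 0.4 | 66.9% |
| 0.5% | 0.2 | 81.8% |
| 0.25% | 0.1 | 90.5% |

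**Step 3. What zero events would show.** The exact (Clopper-Pearson) two-sided 95% upper limit for 0/n is 1 − 0.025^(1/n).
- n = 40: 1 − 0.025^(1/40) = 8.8%.
- n = 20: 1 − 0.025^(1/20) = 16.8%. At a 1% rate the expected count is 0.2 and the chance of at least one event is 18.2%.

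**Step 4. What a commoner bleeding item would give.** The counts here are illustrative, because the questionnaire items and their frequencies are not in the documents. A yes/no item reported by 10 of 40 gives 25% (exact 95% CI 12.7% to 41.2%). The same proportion in 20 women, 5 of 20, gives 25% (8.7% to 49.1%).

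**Step 5. Where each kind of bleeding goes under the plan**

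| Bleeding | Collected | Reported |
|---|---|---|
| Transfused | 8.3.4, day 30 | Named outcome, 9.4.3 |
| Admitted, not transfused | 8.3.4, day 30 | Not in the 9.4.3 outcome; counted under 9.4.4 |
| Other bleeding recorded as a side effect or adverse event | Visit forms | 9.4.4 |
| Bleeding symptoms not so recorded | Questionnaire, Visits 2 and 3 | No planned summary |

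The last row matters because 4.1 describes bleeding as the usual course after misoprostol, and no rule says when it becomes an adverse event.

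**The case against.** The strongest reply is that 9.4.4 already covers bleeding that matters. An admission for bleeding is serious by the definition in 8.3.2, goes to the sponsor at once under 8.3.6, is solicited at day 30, and is tabulated under 9.4.4. That stands. A reader might infer from 9.4.3 alone that such a woman is lost to the report, or that bleeding as a whole goes unestimated; the documents support neither. Transfusion itself receives a proportion with an interval, though an imprecise one.

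Other parts of the reply also stand:
- A reader might call bleeding the regimen's main hazard, but the protocol ranks no hazards.
- The 1% covers all severe adverse events, so 0.4 is a ceiling under an assumption and not a forecast of transfusions.
- Forty women cannot estimate a rare event well under any plan, and 4.1 and 9.1 call the secondary aims hypothesis generating.
- Section 2.3.1 cites abdominal pain at 12%, so a reader might also want cramping of any severity listed. Section 8.3.5 says all patients may have pain during expulsion, and there is no comparator. Naming only severe cramping is defensible, and milder pain reported as a side effect falls under Other.
- The bleeding items have not been seen, so their usefulness is not known.

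What does not stand is that the catch-all settles the matter. It reaches only what someone classifies as a side effect or adverse event. Section 9.4.1 supplies a method for categorical variables and 9.4.9 may not bar a descriptive table, but neither commits anyone to produce one. The sensitivity analysis in 9.3 does bring back excluded women with data, but as the secondary view of a safety question.

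**Conclusion.** The point holds in a limited form. Bleeding below the level of a recorded side effect or adverse event has no prespecified estimate, although the answers are collected. The named outcome is narrower than the solicited event. Under the assumption that transfusion lies within the 1% severe-event rate, it is expected at most about 0.4 times in 40, with at least a 67% chance of none. Zero events would exclude only rates above 8.8% in 40 women, or above 16.8% in 20 adherent completers; the 20 assumes adherence right at the 50% threshold.

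This is a gap in specification and in the choice of main population. It does not show that serious bleeding would go unreported.

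**What to change.** 1. In 9.4.3, define the bleeding adverse event as excess bleeding requiring hospital admission or blood transfusion, and show each component, so that it matches 8.3.4.
2. In 9.4.3, add a table of the existing Visit 2 bleeding-symptom answers (N, %, 95% CI). Show Visit 3 separately and state that its denominator is the selected group with a retained sac who chose medical or expectant management.
3. In 9.3, make all women given UPA with data the main population for side effects and adverse events, with adherent completers as the sensitivity analysis.

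The cost is SAP wording and a few extra table rows. All three changes use data already collected, and none alters treatment or visits. The changes should be fixed before the bleeding answers are looked at.
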